We hypothesize that subjects receiving spray treatment will report an average sore throat score that is one-half as high as those not receiving treatment and that their sore throat pain will be alleviated significantly faster than subjects receiving placebo. We hypothesize that the aspirin tablet combined with the aspirin and/or wintergreen throat spray will decrease sore throat pain as well as improve Jackson scores for common cold symptoms. This hypothesis is based on our own data using human biopsy tissue showing that Treatment decreases inflammatory prostaglandin production by at least 50% without damaging respiratory tissue and is also based on studies of aspirin treatment for the common cold (Glatthaar-Saalmuller et al., 2017). The Treatment will consist of a formulation of active and inactive ingredients listed in the “Additional Information” section of this protocol. The placebo will consist of vehicle buffer, a sub-therapeutic dose of menthol, and a sweetener. The sub-therapeutic dose of menthol is included so the placebo will taste and smell similar to treatment. Since a multitude of mechanisms contribute to the placebo effect, such as expectations, learning, memory, and motivation (Gupta and Verma 2013), we aim to remove as many stimuli as possible from the placebo group to control for these effects.

METHODS

OVERVIEW OF THE STUDY DESIGN

Subjects will be recruited via targeted social media advertisements (Facebook). Subjects interested in enrolling in the study will call a number listed in the ad or fill out an online form and be called back by the Clinical Trial Manager (CTM).

The CTM will ask potential participants a series of questions on the phone to determine their initial eligibility and enter responses on a digital form (CTM Intake Form) contained on a HIPAA-compliant platform.

The CTM will arrange an in-person visit by the Clinical Trial Administrator (CTA) to the participant's home for that evening as well as a virtual visit by the physician (PI) also for that evening. In addition, the CTM will email participants a copy of the Informed Consent (IC) for them to look over. The CTA will collect a signed physical copy of the IC during their visit as well as baseline sore throat assessments.

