Healthy adults between the ages of 18-65 that do not meet any of the exclusion criteria listed below, and who rate their sore throat at least a 3 on a 10 point scale, and who have had a sore throat for less than 48 hours by the time they complete the CTM assessment.

Exclusion

Sore throat for more than 2 full days at the time of CTM assessment

Fever or development of fever during the course of the trial

Positive COVID-19 test or influenza test at CTA visit

Likelihood of strep throat (to be determined by PI to the best of their ability)

Less than 2 doses of the COVID vaccine

Any allergies to eggs, milk, or aspirin

Females who are pregnant or test positive for pregnancy at the CTA visit

Any chronic disease such as asthma, hypertension, post-nasal drip, gastroesophageal reflux disease (GERD), cardiopulmonary obstructive disorder (COPD), diabetes, cancer, HIV

Any history of allergy in the last 14 days for which they took medication

Anyone with fever above 101 or who has taken medication other than birth control in the last 30 days

Anyone taking an ACE inhibitor

Participation in another clinical trial within the last 6 months or during this trial

Anyone who smokes

STATISTICAL CONSIDERATIONS

ANALYSIS PLAN

The design of this study will be a between patient, non-crossover, randomized controlled trial. The primary endpoint of this study is a time-weighted summed difference in pain intensity on the sore throat pain intensity scale over 36 hours after the first dose of medication (STPIS 1st entry Day 1 compared to STPIS 4th entry Day 2). For the study to have 80% power and 20% effect size, we believe we will need at least 100 participants per condition. Our hypothesis is that the patented Mucosal Immune Complex (MIC) will decrease STPIS score by 25-50%. Our assumptions and our hypothesis are based on a previous study utilizing this endpoint with an average baseline STPIS score of 79.1 (+/- 8.2) (Schachtel et al., 2014). Assuming a 50% drop-out or exclusion rate, we aim to enroll a total of 400 participants across all four conditions.

Efficacy will be determined by t-test comparing time-weighted summed differences in STPIS scores for placebo and MIC treatment groups. Secondary endpoints will include changes in STPIS at different time points and changes in Modified Jackson Score over the course of the study.

SAMPLE SIZE JUSTIFICATION

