Based on a similar prior study of an NSAID containing lozenge for sore throat (Schachtel et al., 2014) a 59% decrease in time weighted summed difference for STPIS over 24 hours was seen with a p-value less than 0.01 with a sample size of 198 participants.

PROCEDURES AND DATA COLLECTION

Paper-based Patient Forms will be mailed to a PO Box monitored by the PI and the DA, located in Rockville MD. Survey assessments will be measured in mm from the beginning of the line and recorded on an Excel spreadsheet according to kit number (Participants will not be identified by name).

FOLLOW-UP

Participants will be able to contact the PI, CTA, and CTM at any point during the trial. They will be encouraged to contact the trial staff should they suspect any adverse events including fever above 101 at which point a determination will be made by the PI or AES if they should continue. Participants will not be followed after the study ends. Other serious adverse events that the PI will discuss with participants include nausea or vomiting, difficulty breathing, and/or breaking out in a rash or hives.

If anyone else should require information gathered from this study, they will only receive the participant's code number, age, sex, ethnicity, but no other identifying information.

DATA AND SAFETY MONITORING

Participants will self monitor at home and fill out the survey questionnaire at the required time points. Participants will be encouraged to call 911 in case of emergencies such as anaphalactic shock and high fever. The PI and CTM will be available for questions and non-urgent matters.

The AES will be available to address serious adverse events and will unblind the study in cases such as high fever where the participant may be harmed by being in the placebo group, or for any other medically necessary reason.

DISCONTINUATION OF RESEARCH PARTICIPANTS/WITHDRAWAL

Participants will be able to voluntarily discontinue at any point in the study by calling the CTM.

RECORD RETENTION

In the event of any publication or presentation resulting from the research, no personally identifiable information will be shared.

REPORTABLE EVENTS

As required by Policy IRB-01, all reportable events will be reported to the IRB within the specified deadlines. Additional information is provided in the IRB Guidance on “Reportable Events.” Events are defined in the IRB Guidance on “Acronyms and Definitions.” For additional information see: <http://research.downstate.edu/irb/irb-policies.html>

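### Enrolling 400 with a 50% loss leaves about 50 per condition against a stated minimum of 100, and the 100 cannot be derived from the inputs given

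*Combined protocol and SAP*

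**What the plan says.** The sample size is set in Statistical Considerations, Analysis Plan. The requirement is: "For the study to have 80% power and 20% effect size, we believe we will need at least 100 participants per condition". A few sentences later comes the enrolment target: "Assuming a 50% drop-out or exclusion rate, we aim to enroll a total of 400 participants across all four conditions".

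The same section hypothesises that treatment "will decrease STPIS score by 25-50" per cent, while the Hypotheses section expects scores "one-half as high as those not receiving treatment". The only mean and spread quoted are a baseline of 79.1 (± 8.2) from a previous study. The test is given as: "Efficacy will be determined by t-test comparing time-weighted summed differences in STPIS scores for placebo and MIC treatment groups". The plan does not state alpha, sidedness, allocation ratio or an SD for the endpoint. It does not say whether the three treatments are pooled or each compared with placebo.

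The separate Sample Size Justification section contains no calculation. It reports that a prior study saw a 59% decrease over 24 hours with p below 0.01 in 198 participants.

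On losses, the Discontinuation section says: "Participants will be able to voluntarily discontinue at any point in the study by calling the CTM". The exclusion list also covers fever that develops during the trial.

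**The concern.** Three figures in one paragraph do not fit together: 100 per condition needed, 50% lost, 400 enrolled over four conditions. The 400 is the requirement multiplied by the number of conditions, with nothing added for the loss that the same sentence assumes.

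If 100 per condition is what 80% power requires, the enrolment target does not deliver it at the plan's own loss rate, and the 80% does not describe the trial that will be analysed. A null result could not then be read against the stated power. Nor can a reader work out what difference the trial can detect, because the inputs behind the 100 are incomplete.

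**Working it through.** **Inputs from the plan:** 100 per condition, 80% power, 20% effect size (no scale), 50% drop-out or exclusion, 400 enrolled, four conditions, two-group t-test, baseline 79.1 ± 8.2.

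**Assumed, because not stated:** equal allocation; no outcome data from those lost; two-sided 5%, with one-sided 5% alongside; no multiplicity adjustment.

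**1. The enrolment target**

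- The plan's figure: 4 × 100 = 400. It is reproduced only with no inflation for loss.
- Evaluable per condition after the loss: 400 × 0.5 / 4 = 50.
- Enrolment needed for 100 evaluable: 4 × 100 / (1 − 0.5) = 800.

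**2. Can the 100 be derived?**

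The normal approximation is n per group = 2 (z₁₋α/₂ + z₀.₈)² / d², with (1.960 + 0.842)² ≈ 7.85. Exact t-test results are given where they differ.

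| Reading of the 20% | n per condition |
|---|---|
| Standardised difference d = 0.20 | 2 × 7.85 / 0.04 ≈ 393 (t-test 394) |
| Same, one-sided 5% | 310 |
| 20% of 79.1 = 15.82 mm, with the baseline spread 8.2 used as SD | 2 × 7.85 × (8.2 / 15.82)² ≈ 4.2, so 5 |
| Cohen's f = 0.20, four-group ANOVA | about 70 |
| Cohen's f = 0.20, two groups (d = 0.40) | about 99 |
| 20% of 79.1 = 15.82 mm, with an assumed SD of about 40 mm | about 100 |

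The last two rows come close to 100, but each needs an assumption that the plan does not state. The 8.2 is the spread of a baseline score, not the SD of a time-weighted summed difference.

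**3. What the loss does to power**

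Take the plan at its word that 100 per condition gives 80% power. The noncentral t distribution then gives the implied standardised difference, and the power for that difference at half the size.

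| Comparison | Alpha | Implied d at full size | Power at half size | d detectable with 80% power at half size |
|---|---|---|---|---|
| Pairwise, 100 v 100 → 50 v 50 | two-sided 5% | 0.398 | 0.505 | 0.566 |
| Pairwise, 100 v 100 → 50 v 50 | one-sided 5% | 0.353 | 0.543 | 0.501 |
| Pooled, 300 v 100 → 150 v 50 | two-sided 5% | 0.324 | 0.507 | 0.460 |
| Pooled, 300 v 100 → 150 v 50 | one-sided 5% | 0.288 | 0.544 | 0.407 |

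All four cases give about 50-54%, so the result does not depend on which of these unstated choices was intended. At d = 0.20 (two-sided), power is 29% with 100 per condition and 17% with 50.

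**4. If most of the 50% falls before enrolment**

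With an assumed later loss of 10% (90 per condition) to 30% (70 per condition), pairwise power is 0.757 to 0.648 two-sided, or 0.762 to 0.667 one-sided. The shortfall is smaller but remains.

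**5. Could 50 per condition still be enough for the hypothesis?**

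This is an illustration only. It treats the endpoint as a mean difference in mm for one pairwise comparison (two-sided 5%) and assumes no change on placebo. The largest SD that keeps 80% power is difference / 0.566.

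| Baseline | 20% reduction | 25% reduction | 50% reduction |
|---|---|---|---|
| 79.1 mm (prior study) | 28 mm | 35 mm | 70 mm |
| 50 mm (assumed) | 18 mm | 22 mm | 44 mm |
| 30 mm (assumed) | 11 mm | 13 mm | 27 mm |

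The lower baselines are shown because this trial admits people "who rate their sore throat at least a 3 on a 10 point scale". Whether 50 suffices depends on an SD that the plan does not give.

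**The case against.** The literal reading is not the only one.

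- **The 100 may already include the loss.** 50 × 2 × 4 = 400 reproduces every figure, and the plan says participants, not evaluable participants. This is possible, but the sentence links the 100 to power, and the loss rate appears only afterwards. If this is what was meant, the requirement is 50 evaluable and the plan should say so.
- **The 50% may be mostly exclusion before dosing.** The COVID-19, influenza and pregnancy tests take place at the home visit where consent is signed and kits are handed out, and the study lasts only two days. That would shrink the shortfall. But the plan speaks of enrolling 400, not screening them, and some losses come later by design: fever during the trial, and withdrawal at any time. The 400 has no margin for these.
- **The 100 may not be arbitrary.** Cohen's f = 0.20 for two groups gives about 99. This is a fair point against calling the 100 wrong. It does not make the 100 derivable from what is stated.
- **The SD limits are generous.** If placebo scores also fall, the between-arm difference is smaller than the same percentage of baseline, and the tolerable SDs are lower. A time-weighted sum is not a plain mm difference, and 30 mm treats an entry minimum as a mean. This stands, so the limits are only an illustration and the conclusion does not rest on them.
- **Three treatments against placebo may call for adjustment.** At an illustrative 0.05/3, the detectable d with 50 per condition rises from 0.57 to about 0.66. This stands, and any restated figure must name the comparison and the alpha.

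**Conclusion.** The concern holds and must be fixed. As written, the enrolment target yields half of the plan's own minimum per condition, given equal allocation and no data from those lost. If the 100 is right for 80% power, power at 50 per condition is about 50-54%, whether the test is pairwise or pooled, one-sided or two-sided at 5%. The 100 cannot be verified from the stated inputs.

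Confidence is high that the figures are unreconciled. It is lower that exactly 50 per condition will be analysed, because that depends on when the 50% occurs. Nothing here shows that the trial is underpowered for a 25-50% reduction.

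**What to change.** First, the sponsor should state whether the 50% falls before or after enrolment, and whether the 100 already includes it. The wording then follows from the answer.

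- **If the loss comes after enrolment and 400 is kept**, restate the claim along these lines: 400 enrolled with 50% loss gives about 50 evaluable per condition, which has 80% power for a standardised difference of about 0.57 (two-sided 5%, one pairwise comparison; alpha and sidedness to be confirmed). If the primary test pools the three treatments, the figure is about 0.46 (150 v 50). With one-sided 5%, the figures are about 0.50 pairwise and 0.41 pooled.
- **If the 100 was meant to include the loss**, state that 50 evaluable per condition is the requirement.
- **If most of the 50% is exclusion before enrolment**, say so and give the loss expected afterwards.

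In every case, replace the 20% effect size with a difference in mm and an SD for the time-weighted summed difference. State alpha, sidedness, allocation, and whether the comparison is pooled or pairwise, with any adjustment for three comparisons.

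Keeping 400 costs protocol wording only, with no added participants. The price is a larger detectable difference: about 0.57 instead of 0.40 (pairwise, two-sided 5%). The sponsor must supply the SD and judge whether that difference is plausible. Keeping 100 evaluable per condition would instead mean enrolling 800, that is 400 more.

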The CTA will collect vital signs from each participant during the in-person visit and fill out digital forms (CTA Intake Form). The CTA will also provide the participants with study materials and randomly assigned and double-blinded interventions or placebo.

Subjects will be randomized with respect to which treatment or placebo they receive, and whether they get the placebo or treatment spray or lozenge. The spray will be applied every hour during waking hours and the tablet will be taken every four hours during waking hours. Subjects will be asked not to eat or drink anything for a few minutes after administration.

Subjects will be asked at four-hour intervals during waking hours to rate their sore throat pain on a validated, paper-based sore throat pain scale, Sore Throat Pain Intensity Scale (STPIS) consisting of a 100mm line along which participants mark their pain intensity (Schactel et al., 2014 and references therein).

The study will end when participants complete their second day of treatment and surveys.

The study will be conducted in a double-blind format, neither the participant nor the CTA, CTM, or PI will know whether the participants are getting treatment or placebo. Participants will be coded and randomized by a third party as the treatments are bottled.

The study will only be unblinded at the end of the study after the data analysis has been completed and by the Adverse Events Specialist (AES) in the case of adverse events.

STUDY POPULATION

Healthy adults, half male, half female, aged 18-65 with no history within the past 30 days of serious allergy, asthma, nasal or otologic disease, and no symptoms of upper respiratory infection (URI). After age 65 many of the exclusion criteria listed below become more common. We feel it is important to enroll an equal number of males and females to control for gender bias in the data.

This will be controlled for in the recruitment process and adjusted if needed by controlling social media targeting criteria. Initially the target population will be: age 18-65, living in the Washington DC/northern Virginia area, retired, government employee, teacher, non-active duty military personnel, or college student.

INCLUSION AND EXCLUSION CRITERIA

Inclusion

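### The primary t-test does not use the collected baseline pain score as a covariate; adjusting the same endpoint for it is a cheap, optional precision improvement of uncertain size

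*Combined protocol and SAP*

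**What the plan says.** The Analysis Plan (Statistical Considerations) defines the primary endpoint as a time-weighted summed difference in STPIS "over 36 hours after the first dose of medication", glossed as "STPIS 1st entry Day 1 compared to STPIS 4th entry Day 2". The test is stated in one sentence: "Efficacy will be determined by t-test comparing time-weighted summed differences in STPIS scores for placebo and MIC treatment groups". No covariate, ANCOVA or other baseline adjustment appears anywhere.

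Baseline pain is nevertheless recorded. In the Overview of the Study Design, the home visit collects the consent form "as well as baseline sore throat assessments"; the instrument is not named. The same section sets the later ratings: "Subjects will be asked at four-hour intervals during waking hours to rate their sore throat pain".

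The expected effect is put in proportional terms twice. The Hypotheses section expects "an average sore throat score that is one-half as high as those not receiving treatment", and the Analysis Plan expects that the product "will decrease STPIS score by 25-50" per cent. The only baseline spread in the documents comes from the cited prior study, an "average baseline STPIS score of 79.1 (+/- 8.2" on the 100 mm scale).

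**The concern.** Subtracting the first entry uses baseline, but with its slope fixed at 1. If pain falls by a fraction p of its starting level, the drop is p times baseline, so the difference still depends on baseline with a slope of about p. On the stated hypotheses that slope would be about 0.25 to 0.5 on treatment, and probably smaller on placebo. The t-test leaves this variation in its error term.

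What is at stake is precision, and only modestly. The plan loses 50% of participants and keeps about 50 per condition, so a narrower interval at no data cost is worth considering.

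A related gap is that the documents do not say which value is the pre-dose baseline. If four-hourly entries start at the same clock time on both days, the first Day 1 entry to the fourth Day 2 entry spans 24 h + 3 x 4 h = 36 h, which matches the stated window. The first entry then falls at the first dose, but nothing says that it is recorded before that dose.

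**Working it through.** The plan gives no precision figure for this point, so there is none to reproduce.

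**Inputs from the documents.** 400 enrolled, 50% loss and four conditions give 400 x 0.5 / 4 = 50 analysable per condition. Baseline mean is 79.1 and SD 8.2 (the figure after +/- is read as an SD). The entry floor is 3 on a 10-point scale.

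**Assumptions.** Equal allocation; residual SD of the time-averaged difference 15-20 mm; baseline slopes 0-0.5 on placebo and 0-0.75 on treatment; as a wider alternative, baseline uniform on 30-100 mm.

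**1. Same effect.** With baseline centred at the mean of all analysed participants, the adjusted contrast targets the same mean difference. In simulation with a true difference of 8.0, the t-test and the ANCOVA averaged 8.03 and 8.03 with an uninformative baseline, and 7.98 and 7.98 with unequal slopes.

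**2. Expected cost if baseline is uninformative.** With k conditions and n analysable in each, variance rises by (1 - 1/k)/(n - 3).
- n = 50: 0.75/47 = 1.6%, about 0.8% of the standard error.
- n = 30: 0.75/27 = 2.8%.
- n = 100: 0.75/97 = 0.77%.
- n = 50 with a strongly skewed baseline: 1.8% (simulated).

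**3. Break-even.** Setting (1 - r²)(1 + 0.75/47) = 1 gives a correlation r of about 0.13 between baseline and the difference. With slope 0.25 in both arms and SD 8.2, r = 2.05/√(2.05² + 15²) = 0.14 or 2.05/√(2.05² + 20²) = 0.10, close to break-even. With slope 0.5, r = 0.26 or 0.20.

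**4. Variance relative to the t-test.** 100,000 simulated four-arm trials per scenario, 50 per arm, one slope per condition, pairwise and pooled contrasts. Ranges cover residual SDs 15 and 20.

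| Placebo slope, treated slope | Baseline SD 8.2 | Uniform 30-100 mm |
|---|---|---|
| 0, 0 | 1.014-1.015 | about 1.016 (step 2) |
| 0, 0.25 | 1.009-1.016 | 0.974-1.011 |
| 0, 0.5 | 0.990-1.014 | 0.873-1.000 |
| 0.25, 0.25 | 0.998-1.008 | 0.911-0.956 |
| 0.25, 0.5 | 0.977-1.000 | 0.802-0.923 |
| 0.25, 0.625 | 0.956-0.995 | not tabulated |
| 0.5, 0.5 | 0.946-0.978 | 0.701-0.811 |
| 0.5, 0.75 | 0.907-0.965 | not tabulated |

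The pairs (0, 0.5), (0.25, 0.625) and (0.5, 0.75) represent a treated score that is half the placebo score: treated slope = 1 - 0.5 x (1 - placebo slope).

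**5. The interval that would be reported.** Sampling variance is not the same as the width of the printed interval, so that was simulated too.
- HC3 standard errors with the centring term, SD 8.2: wider than the t-test interval in 12 of 16 scenarios, from 2.6% wider to 3.1% narrower.
- HC2 with the centring term, SD 8.2: from about 0.5% wider (baseline uninformative) to about 5% narrower (slopes 0.5 and 0.75, residual SD 15). Non-coverage was 4.9-5.4%.
- HC2, uniform 30-100 mm: up to about 23% narrower.

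**6. Why one slope per condition.** With placebo slope 0, a common-slope ANCOVA of a pooled 150 v 50 contrast loses 0.8-2.1% of variance at SD 8.2 and 1.6-8.6% at the wide spread.

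**7. Chance imbalance.** The 95% range of the baseline difference, 50 v 50, is 1.96 x 8.2 x √(2/50) = 3.2 mm. At slopes 0.25-0.5 it moves the result by 0.8-1.6 mm. The residual half-width is 1.96 x 15 x 0.2 = 5.9 mm or 1.96 x 20 x 0.2 = 7.8 mm. In quadrature the imbalance adds 0.04-0.22 mm to it, and the t-test's standard error already includes this.

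**The case against.** The strongest reply is that the endpoint already subtracts baseline, the t-test is valid under randomisation, and at the only documented spread the change is close to zero and of uncertain sign. Most of this stands. With placebo slope 0 and SD 8.2, the variance runs from 1.6% worse to 1.0% better. Every larger gain needs a non-zero placebo slope or the wider spread, which the documents do not give. The simulation model is also not capped at 100 mm, so the wide-spread figures are rough. If the whole hypothesised 25-50% is a difference from placebo, power is already ample.

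The choice of standard error matters as well: HC3 would usually widen the interval at SD 8.2. HC2 removes that problem.

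A reader might infer more than the documents support:
- *That the t-test is biased or invalid, or that chance imbalance is a separate defect.* It is neither; step 7 shows that imbalance is already in the standard error.
- *That 1.6% is the most that adjustment can cost.* It is the expected cost at exactly 50 in each of four equal conditions. The allocation ratio is not stated, and the 50% loss is the sponsor's own assumption.
- *That a gain is assured, or would make good the shortfall from the stated 100 per condition.* No baseline-endpoint correlation or endpoint SD is given.

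**Conclusion.** The point holds as an optional, cheap efficiency improvement. The plan collects baseline pain and leaves it out as a covariate. A centred ANCOVA with one slope per condition and HC2 standard errors estimates the same effect at little expected cost: the interval is about 0.5% wider if baseline is uninformative.

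Under the assumed residual SDs and slopes, with 50 analysable in each of four equal conditions, the possible gain is near zero to about 5% of interval width at SD 8.2. It is larger only if this trial's baseline is much more spread out. The entry floor of 3 out of 10 permits that but does not establish it. All these figures use the subtracted first entry as the covariate. Neither gain nor cost has been evaluated for the home-visit assessment.

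**What to change.** Replace the t-test sentence in the Analysis Plan with a prespecified ANCOVA:
- Outcome: the same time-weighted summed STPIS difference.
- Terms: condition (four levels), the pre-dose pain score centred at the mean of all analysed participants, and one baseline slope per condition.
- Estimate: the treatment-minus-placebo contrast(s). The model serves pooled or separate comparisons; the plan should say which is primary.
- Standard errors: HC2, not HC3. Add the centring term, (difference between the two slopes)² x baseline variance / number analysed, to the variance. For a pooled contrast, use the average treated slope.
- Covariate: state whether the first Day 1 entry is recorded before the first dose. If it is, use it. If not, use the home-visit baseline assessment and name its instrument. Never adjust for a post-dose entry.
- Missing covariate: fill with the overall mean, not the arm mean.

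The cost is SAP wording, a few lines of code and four degrees of freedom; no new data are needed. No participant is lost if the first entry is the covariate, because without it there is no endpoint. If the home-visit value is used, the overall-mean rule keeps everyone in. The change should be made before unblinding, so that the covariate cannot appear to have been chosen on the results.

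### The plan expects 50% loss but does not say how a 36-hour sum is formed from a partial diary; a complete-diary t-test could be biased either way and lose up to about 48% of the usable information

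*Combined protocol and SAP*

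**What the plan says.** Under Statistical Considerations, Analysis Plan: "The primary endpoint of this study is a time-weighted summed difference in pain intensity on the sore throat pain intensity scale over 36 hours", counted from initial dosing, with the parenthesis "STPIS 1st entry Day 1 compared to STPIS 4th entry Day 2". The test is a single sentence: "Efficacy will be determined by t-test comparing time-weighted summed differences in STPIS scores for placebo and MIC treatment groups". No covariate is named.

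The diary is described under Overview of the Study Design: "Subjects will be asked at four-hour intervals during waking hours to rate their sore throat pain". The parenthesis implies four entries a day, so eight in all.

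On loss, the Analysis Plan says: "Assuming a 50% drop-out or exclusion rate, we aim to enroll a total of 400 participants across all four conditions". The 50% is not divided between drop-out and exclusion. Fever arising during the trial is listed as an exclusion, so some exclusions can follow randomisation. Paper forms come back by mail, and participants may withdraw at any time.

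The document has no rule for a missing entry, no analysis set, no imputation and no sensitivity analysis. STPIS at different time points is a secondary endpoint with no model named.

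**The concern.** A t-test on a summary needs that summary for every person analysed. A 36-hour sum is undefined for someone who stops at hour 12 or skips a rating, unless a rule says how to fill the gap. Without one, the analyst must choose between completers, carrying values forward or imputing, possibly after seeing the data. Completers are the path of least effort.

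Two things are then at stake. Sore throat resolves quickly, so people may stop because they are well or because they are not improving. If stopping depends on pain, completers are a selected group, and the selection may differ between arms. Ratings recorded before stopping are also left unused. Both matter more when half the participants may be lost. The point concerns entries already collected, not whether further ratings should be sought after someone stops.

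**Working it through.** **1. The plan's own figure.** The plan says: "For the study to have 80% power and 20% effect size, we believe we will need at least 100 participants per condition". With two-sided alpha 0.05 (assumed; none is stated), n per arm = 2(1.96 + 0.8416)²/d² = 15.70/d².
- d = 0.2: 15.70/0.04 = 392.4, so 393 per arm.
- 20% of the quoted baseline: 0.20 × 79.1 = 15.82 mm; 15.82/8.2 = 1.93 SD; n = 5 per arm.
- d = 0.4: 15.70/0.16 = 98.1, so 99. This comes close to 100, but 0.4 is not in the document.

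The figure does not reproduce from the stated inputs. Nor is the loss built in: 400/4 = 100 enrolled per condition (equal allocation assumed), and 100 × 0.5 = 50 remain. Inflating for the loss would need 100/0.5 = 200 per condition, 800 in all. These are separate and larger problems; here they only set the scale.

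**2. Skipped entries.** If the endpoint is the full sum, with seven entries after the first, and each is missed at random with probability q, the share with a complete sum is (1 − q)^7.
- q = 5%: 0.95^7 = 0.698, or 70%.
- q = 10%: 0.90^7 = 0.478, or 48%.

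If the parenthesis means a first-versus-last difference, these figures do not apply, although early stoppers still lack the last entry.

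**3. Information lost by using complete diaries only.** Assumed inputs: entries at 0, 4, 8, 12, 24, 28, 32 and 36 h; 50% complete; drop-out at random and permanent; five correlation structures (exchangeable 0.5 and 0.7, AR(1) 0.8 and 0.9, and a mixture). Let c be the weights of the sum, S the covariance of the entries, p_k the share whose diary ends at entry k, and S_k the covariance up to that entry.
- Complete diaries: V_cc = c′Sc/0.5.
- All entries: V_all = c′(Σ p_k S_k⁻¹)⁻¹c, each S_k⁻¹ padded with zeros.
- Loss = 1 − V_all/V_cc.

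| Make-up of the 50% loss | Even timing | Late | Early |
|---|---|---|---|
| All drop-outs with a partial diary | 40–43% | 47–48% | 30–35% |
| Half have no diary | 26–28% | 31% | 19–23% |
| None have a diary | 0% | 0% | 0% |

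As a check on the ceiling, if every lost person supplied almost a full diary, the loss would approach 1 − 0.5/1.0 = 50%. If half of them did, it would approach 1 − 0.5/0.75 = 33%.

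This is not merely the benefit of baseline adjustment. Against a completer analysis that also adjusts for baseline, the top row becomes about 37–39%, 46–47% and 22–27%.

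**4. What that means for power.** Power ≈ Φ(d√(n/2) − 1.96), with d = 0.4 for illustration:
- 50 complete diaries per arm: 0.4 × √25 − 1.96 = 0.04, or 52%.
- 25% recovered: effective n = 50/0.75 = 67; 0.4 × √33.5 − 1.96 = 0.36, or 64%.
- 40% recovered: effective n = 50/0.60 = 83; 0.4 × √41.5 − 1.96 = 0.62, or 73%.

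**5. Bias (illustrative simulation).** Drop-out depended on the last recorded pain.

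Set-up A: effect 18 mm with gradual onset, baseline mean 70, about 50% lost. Change in the completer estimate relative to the truth:
- unrelated to pain: about 0%;
- high-pain participants leave, both arms: −2% to −7%;
- recovered participants leave, both arms: −1% to −12%;
- placebo leaves for pain, active on recovery: −21%;
- placebo leaves on recovery, active for pain: +16%.

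Set-up B: 100 per arm, baseline mean 60 and SD 15, true effect 8 mm. With opposite mechanisms completers gave about 3.4 mm or 11.4 mm. A likelihood model of all entries stayed near 8 mm throughout, and completer variance was 1.3 to 1.9 times as large.

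**The case against.** The strongest reply is that the plan is silent rather than wrong. A t-test can follow interpolation or multiple imputation, and the document excludes neither. This stands. A reader might infer that the plan discards every partial diary, but that is only the likely default.

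Second, the 50% mixes drop-out with exclusion. COVID, influenza and pregnancy tests take place at the administrator's home visit, so some of those excluded may have no post-dose entries, and an unreturned paper form loses the whole diary. No model recovers anything from such people. This also stands, and it is why the range starts at 0%. A reader might settle on about 40%, but that needs nearly all the loss to be drop-out with a usable diary.

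Third, one might read the 50% sentence as deducting the loss from the number analysed, so that partial diaries count as no data. The plan's arithmetic contradicts this: 400/4 = 100, so nothing is deducted.

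Fourth, the simulation inputs are not the plan's. The hypothesis is that treatment "will decrease STPIS score by 25-50" percent, which from 79.1 is about 20 to 40 mm. With the standard error of 2.53 mm that set-up B gave under random loss, 20/2.53 is about 8, so power would be near 100% even with completers. If the effect is that large, the efficiency argument has little weight. But the plan gives no SD for the sum, so that standard error is itself assumed, and extra power does not remove bias.

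**Conclusion.** The concern holds in limited form. The document establishes three things: a single unadjusted t-test on one 36-hour value per person, an expected 50% loss, and no rule for partial diaries. If only complete diaries are used, the loss of usable information lies between 0% and about 48%, depending on the unstated split of the 50%, the timing of drop-out and the correlation between entries.

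Bias arises when stopping depends on recorded pain, and its direction is unknown. A reader might expect the effect to shrink, because it does when the same mechanism acts in both arms. It can equally be inflated when arms leave for opposite reasons, and random loss gives no bias. The simulated sizes are illustrations, not forecasts. Using partial diaries would not repair the sample size.

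**What to change.** Replace the t-test sentence with the following, in substance:
- **Analysis set:** all randomised participants with a baseline STPIS and at least one later entry; nobody is dropped for a missing entry.
- **Model:** repeated measures of all post-dose STPIS entries, with condition by entry, baseline by entry and unstructured covariance.
- **Primary estimate:** the time-weighted linear combination of the condition-by-entry mean differences from placebo, with 95% CI.
- **Sensitivity:** one delta-adjusted analysis for departures from missing at random.

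State as well whether the endpoint is the full sum or a first-versus-last difference.

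Multiple imputation using all entries, followed by a baseline-adjusted comparison of the sum, is an acceptable equivalent. The repeated-measures model has the advantage of also giving the secondary results at individual time points.

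The cost is SAP wording and a little more analysis work, with no new data. The small downside is reliance on missing at random, which the sensitivity analysis tests.
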